6.2. Vital Signs

Blood pressure, pulse, and body temperature will be measured at screening; at randomization; every 3 months after randomization through Month 12, then every 6 months through Month 54 (or early termination). At each visit, blood pressure and pulse will be measured in both supine and standing positions. Weight will be measured at screening; at randomization; then every 6 months after randomization through Month 54 (or early termination). Height will be measured at screening and Month 54 (or early termination).

Continuous vital sign variables including pulse, blood pressure (systolic and diastolic), temperature, weight, and Body Mass Index (BMI) will be summarized with descriptive statistics at each on-treatment time point and for the on-treatment endpoint. BMI will be calculated as $[\text{weight (kg)} / (\text{height (m)})^2]$ at each time point that body weight is measured. The height measurement collected at screening will be used in the calculation. Changes from baseline will be summarized for each on-treatment time point and for the on-treatment endpoint. Descriptive statistics (mean, standard deviation, median, minimum and maximum) will be presented. Weight will be plotted over time for the on-treatment period and for the off-treatment period.

Incidence of treatment-emergent potentially clinically important abnormalities in vital signs while on treatment, as defined in [Table 4](#), will be summarized for subjects who had a baseline assessment and at least one post-baseline, on-treatment assessment for that vital sign. The incidence will also be summarized for the off-treatment visits.

For off-treatment period, the vital sign variables will be similarly summarized.

Table 4: Potentially Clinically Important (PCI) Criteria for Vital Signs

Vital sign	Criteria for Low PCI Values	Criteria for High PCI Values
Systolic BP (mmHg)	< 90	>180
Diastolic BP (mmHg)	<50	>105
Pulse (bpm)	<50	>120
Temperature (C)	<36	>38
Weight (kg)	Decrease of 10% relative to baseline	Increase of 10% relative to baseline
Orthostatic hypotension	A decrease in systolic (>20 mm Hg) or diastolic (>10 mm Hg) blood pressure after standing for at least 2 minutes relative to supine position with an increase in pulse rate of >15 beats per minute.	

6.3. Electrocardiogram (ECG)

ECGs will be performed at screening; at randomization; after randomization at Month 1, Month 3, and Month 6; then, every 6 months through Month 54 (or early termination).

The ECG variables that will be analyzed are heart rate, PR interval, RR interval, QRS interval, QT interval, and QTc using the following correction methods:

- Bazett's formula: $QTcB \text{ (msec)} = QT \text{ (msec)} / (60/HR(\text{bpm}))^{1/2}$;
- Fridericia's formula: $QTcF \text{ (msec)} = QT \text{ (msec)} / (60/HR(\text{bpm}))^{1/3}$;
- Linear Derived formula: $QTcLD(\text{msec}) = QT(\text{msec}) + \beta * (1-60/HR(\text{bpm}))$, where β is the estimated slope derived from the linear regression model $QT(\text{msec}) = \alpha + \beta * 60/HR(\text{bpm})$ using all observations prior to treatment initiation of all subjects excluding screen failures;
- Sagie formula: $QTcI \text{ (msec)} = QT(\text{msec}) + 154 * (1 - 60/HR(\text{bpm}))$

QTcB and QTcF will be provided by the central ECG vendor and not recalculated. Triplicate ECGs, completed within a 4-minute time period, are collected at each visit. The value for each parameter on a given date will be the average of the values obtained from the triplicate ECGs.

Descriptive statistics will be presented by treatment group for the above ECG variables at each scheduled time point and for the on-treatment endpoint. Change from baseline to each scheduled on-treatment time point and to the on-treatment endpoint will be descriptively summarized by treatment group. For off-treatment visits, change from the off-treatment baseline (see Section 2.4) will also be calculated.

The number and percentage of subjects with treatment-emergent potentially clinically important ECG values as defined in [Table 5](#) below will be presented for each on-treatment time point by treatment group.

Table 5: Potentially Clinically Important (PCI) Criteria for Selected ECG Parameters

Parameter	Criteria for Low PCI Values	Criteria for High PCI Values
HR	< 50	> 100
PR	< 120	> 200
QRS	< 70	> 120
QT		> 500

The number and percentage of subjects with corrected QT values within each of the categories defined below will be presented for the maximum post-baseline, on-treatment value and for each on-treatment time point by treatment group.

- QTc Interval:
 - Males
 - ≤ 450 msec
 - > 450 to ≤ 480 msec
 - > 480 to ≤ 500 msec

- >500 msec
- Females
 - ≤ 470 msec
 - >470 to ≤ 500 msec
 - >500 msec
- QTc change from baseline
 - ≤ 30 msec
 - >30 – 60 msec
 - >60 msec

The distribution of the investigator interpretations (not evaluable; normal; abnormal, not clinically significant; abnormal, clinically significant) will be summarized at each on-treatment time point and for the on-treatment endpoint.

In addition, the number and percentage of subjects with ECG abnormalities according to the central ECG vendor interpretation will be summarized by type of abnormality (conduction, rhythm, etc.) and specific diagnosis for the double-blind phase. Listings for subjects with a corrected QT value >450 for males or >470 for females or change from baseline >30 will be provided.

Similar analyses will be performed for the off-treatment period.

6.4. Other Safety Parameters

6.4.1. Assessment of Psychological Well Being

The Assessment of Psychological Well Being, which includes the 15-item short version of the Geriatric Depression Scale (GDS-15)²³ and the 6-item short version of the state scale of the State-Trait Anxiety Inventory (STAI)⁹, will be performed during screening; at randomization; and after randomization at Month 3, Month 9, then every 3 months through Month 39, then at Months 45, 48, and 54 (or early termination).

The GDS-15 is a subset of items from the GDS-30 (see Section 4.1.6). The items included in the GDS-15 and the scoring for each item are shown in Attachment 3. The GDS-15 total score is the sum of the 15 individual item scores. Higher scores indicate greater levels of depression.

For the STAI, subjects are read 6 statements related to anxiety (“I feel calm”, “I am tense”, “I feel upset”, “I am relaxed”, “I feel content”, and “I am worried”) and asked to rate how they feel “right now, at this moment” on a 4-point scale (“not at all” = 1, “somewhat” = 2, “moderately” = 3, “very much” = 4). The STAI total score is the sum of the individual scores after reverse-scoring the “calm”, “relaxed”, and “content” items. Higher scores indicate more anxiety.

Item scores for both scales are recorded in an electronic device which will provide the total scores for both scales.

Change from baseline will be calculated for both total scores at each time point. Values and changes from baseline at each time point will be summarized for both total scores with descriptive statistics by treatment group. For off-treatment visits, change from the off-treatment baseline (see Section 2.4) will also be calculated and summarized with descriptive statistics.

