### *Safety Analyses*

Safety will be assessed in subjects who received at least 1 dose of study drug. The incidence of AEs will be summarized for each treatment group by body system and preferred term. Changes from baseline in clinical laboratory values, vital signs measurements, body weight, and ECG variables will be presented descriptively. The QT interval corrected for heart rate (ie, QTcF) will be summarized using frequency tabulations. For C-SSRS, the percentage of subjects with a suicide-related outcome will be summarized in incidence and shift tables. Dermatological examination findings, physical and neurological examination findings, and results from the Assessment of Psychological Well Being questionnaire for each scheduled time point will be summarized using frequency tabulations of abnormalities.

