**9.5.7. Assessment of Psychological Well Being**

The Assessment of Psychological Well Being, which is a combination of the GDS (short version) and State-Trait Anxiety Inventory (short version), will be used to monitor for anxiety and depression and will be completed for all subjects as part of the screening evaluations (see Section 9.1.2) as well as during the double-blind treatment phase, ET visit, and follow-up phase (see Time and Events Schedule). The screening assessment must be reviewed prior to scheduling any amyloid biomarker measurement and disclosure of amyloid result by a physician (see Section 9.1.2).

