**Assessment of Psychological Well Being**

Results from the Assessment of Psychological Well Being questionnaire for each scheduled time point will be summarized using frequency tabulations of abnormalities.

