4.1.6. Geriatric Depression Scale (GDS)

The GDS is a 30-item measure used to identify depression in elderly individuals²³. The 30-item GDS is collected during screening only. Each item is answered ‘yes’ or ‘no’ and scored as 0 or 1 according to the table in [Attachment 3](#). The GDS-30 total score is the sum of the 30 individual item scores. Item scores are recorded on an electronic device which will provide the total score.

The GDS-30 total score will be categorized as follows:

- Normal (GDS-30 total score ≤ 9)
- Mildly Depressed (GDS-30 total score 10 to 19)
- Severely Depressed (GDS-30 total score ≥ 20)

The GDS-30 total score will be summarized with descriptive statistics by treatment group and overall and the number and percentage of subject in each GDS-30 total score category will also be summarized by treatment group and overall.

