4.1.7. Assessment of Psychological Well Being

The Assessment of Psychological Well Being is composed of the 15-item short version of the Geriatric Depression Scale (GDS-15) and the 6-item short version of the State-Trait Anxiety Inventory (STAI). See Section [6.4.1](#) for additional details. The total scores of each scale during screening will be summarized with descriptive statistics by treatment group and overall.

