In addition, other adverse event clinical MedDRA PT clusters will be summarized by treatment during the on-treatment phase and off-treatment phase of the study (including but not limited to rash related, sleep disorder related, depression related, anxiety related adverse events).

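### SAP 6.4.1 drops the protocol's tabulation of abnormal results for the depression and anxiety questionnaire, so the number of subjects whose score becomes abnormal after dosing is not reported

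*SAP*

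**What the plan says.** The protocol states the analysis twice. Section 11.10, in its paragraph on this instrument, reads: "Results from the Assessment of Psychological Well Being questionnaire for each scheduled time point will be summarized using frequency tabulations of abnormalities". The Synopsis, under Safety Analyses, repeats it: "results from the Assessment of Psychological Well Being questionnaire for each scheduled time point will be summarized using frequency tabulations of abnormalities". Protocol 9.5.7 gives the purpose; the instrument "will be used to monitor for anxiety and depression and will be completed for all subjects as part of the screening evaluations" and is repeated during treatment, at early termination and at follow-up.

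SAP 6.4.1 describes the same instrument as GDS-15 plus the six-item STAI. Its analysis is: "Values and changes from baseline at each time point will be summarized for both total scores with descriptive statistics by treatment group". Changes from the off-treatment baseline are handled in the same way. For screening, SAP 4.1.7 says: "The total scores of each scale during screening will be summarized with descriptive statistics by treatment group and overall".

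The only depression categories in the SAP are in 4.1.6, where "the number and percentage of subject in each GDS-30 total score category will also be summarized". They apply to the 30-item GDS, which is given at screening only.

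Under Adverse Events in its safety section, the SAP also plans summaries by treatment of clusters that include "rash related, sleep disorder related, depression related, anxiety related adverse events".

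**The concern.** The protocol promised a count of abnormal results for a scale that every subject completes so that depression and anxiety can be monitored. The SAP replaces that count with summaries of the score distribution. For a safety scale in subjects without significant current psychiatric illness, the useful question is usually how many subjects became abnormal, in which arm, and whether this happened on or after treatment. A distribution summary does not answer it.

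The trial was stopped early, and the SAP introduction says that the efficacy objectives can no longer be evaluated. Safety description is the main use left for the data, so omitting a safety output that the protocol names deserves correction or an explanation.

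**Working it through.** Neither document gives a threshold, sample size or power for GDS-15 or STAI, so there is no planned figure to reproduce. The check is mainly textual.

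**Do descriptive statistics include counts in this SAP?** No.
- SAP Table 2 (4.1.1) defines descriptive statistics as N, mean, SD, median and range, and lists frequency distributions as a separate summary type.
- SAP 4.1.6 asks for descriptive statistics of GDS-30 and, in addition, the number and percentage per category. When the SAP wants counts, it says so.

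**Did early stopping remove such counts generally?** No.
- The Synopsis sentence that requires the tabulation covers four items: dermatological findings, physical findings, neurological findings and this questionnaire. The amended SAP keeps counts or distributions for the first three (6.4.4 to 6.4.6).
- It also keeps counts for laboratory values, vital signs, ECG and C-SSRS.
- Among the four items, only the questionnaire loses its tabulation, and no reason is given.

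**Illustration of direction only.** From the SAP, 557 subjects were randomized 1:1:1, so 557/3 = 185.7, or about 186 per arm. The affected fraction, size of rise, SD and background rate are my assumptions.
- Mean shift = fraction affected × rise. With 5% (186 × 0.05 = 9.3 subjects) and a rise of 5 GDS-15 points, the shift is 0.05 × 5 = 0.25. For an SD of 2 to 3, that is 0.25/2 = 0.125 SD down to 0.25/3 = 0.083 SD.
- Standard error of a difference = SD × √(2/186). This is 0.207 for SD 2 and 0.311 for SD 3, so the ratios are 1.21 and 0.80, and power at two-sided 0.05 would be about 23% and 12%.
- The SD would widen too. If SD among the others is 2, the arm's SD becomes √(4 + 25 × 0.05 × 0.95) = √5.19 = 2.28.
- Count, if every affected subject crosses the cut-off: with a 2% background, 186 × 0.07 = 13.0 against 186 × 0.02 = 3.7 (power about 64%). With a 5% background, 186 × 0.10 = 18.6 against 9.3 (power about 45%).
- Range: with 3% to 10% affected and rises of 4 to 6 points, the mean shift runs from 0.03 × 4 = 0.12 to 0.10 × 6 = 0.60. At the top of that range with SD 2, the mean difference would have power of about 83%, so means are not blind to a large effect.
- STAI (six items scored 1 to 4, range 6 to 24): 5% rising 6 to 8 points moves the mean 0.3 to 0.4.

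**Denominators.** 186 is the number randomized, not the number at a visit. The SAP says 447 of 557 had 12 months of treatment or less, which leaves 110, or about 37 per arm, beyond that.

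**Schedule.** SAP 6.4.1 places the scale at Months 3 and 9, every 3 months to Month 39, then Months 45, 48 and 54. The row in the protocol's Time and Events Schedule reads as Months 3, 9, 15, 21, 27, 33, 39, 45, 51 and 54, that is, 6-monthly after Month 9. The table was read by a program, so the columns should be confirmed against the source.

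**The case against.** The strongest reply has four parts.

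1. **The SAP does not report means alone.** It summarizes values and changes, and where it spells out descriptive statistics they include SD, median and range. A wider SD or a higher maximum in one arm would be visible. This stands. A reader might infer that a small affected group would vanish from the output, and the documents do not support that. What would be missing is the number of such subjects: a maximum shows one subject, and an SD does not translate into a count.

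2. **Clinical cases are counted elsewhere.** Depression- and anxiety-related adverse event clusters are summarized by treatment, on and off drug, and C-SSRS is tabulated by category with treatment-emergent criteria. This also stands, and it limits the gap to subjects with a raised score and neither a reported event nor suicidal ideation. That group need not be empty. Protocol 9.5.7 has no instruction to record a raised post-baseline score as an adverse event, whereas 9.9.4 and 9.9.6 have one for examinations and laboratory results.

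3. **Numerical demonstrations rest on assumptions.** No test of this scale is planned, so calling the comparison null, or quoting a z value, describes something the SAP does not do. A clean split with no placebo cases is not supported either. Exclusion criterion 10 admits subjects with minimal symptoms, neither criteria list has a GDS limit, and the SAP provides for depressed categories at screening. Low baseline scores are an inference.

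4. **The protocol defines no abnormal score and leaves detail to the SAP.** That is correct, and it means the output cannot simply be reinstated. But leaving detail to the SAP invites a definition of abnormal; it does not explain removing the tabulation. Halving the GDS-30 threshold to obtain one has no support in the documents, because GDS-15 is a chosen subset of items.

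**Conclusion.** The mismatch holds. Following the SAP as written leaves out a safety output that the protocol states in two places, and the number of subjects whose GDS-15 or STAI total becomes abnormal after dosing would not be reported. The omission is unexplained, and early stopping does not account for it.

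The practical consequence is limited. It concerns subjects with a raised score only, in a trial stopped for hepatic findings, and it touches no efficacy conclusion. The documents do not show that depression or anxiety on drug would go unseen, nor that any harm occurred.

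The illustration (arm mean moving 0.25 points against counts of about 13 to 4, or 19 to 9) depends on the assumed arm size, SD, affected fraction and background rate, and on all cases falling at one fully attended visit. It shows direction, not a forecast. The schedule discrepancy is a separate, smaller inconsistency.

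**What to change.** Reconcile SAP 6.4.1 with Protocol 11.10 and the Synopsis:

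- For the on-treatment and off-treatment periods, add the number and percentage of subjects with an abnormal GDS-15 total and with an abnormal STAI total, by treatment group, at each time point and at the worst post-baseline value. Add a shift table from the relevant baseline. The worst-value table gathers cases that scatter across thinly attended visits.
- Keep the descriptive summaries already planned.
- Have the sponsor prespecify and justify a definition of abnormal for each scale before unblinding. Neither document contains one, and none is proposed here.
- If the sponsor prefers not to tabulate, state the departure from the protocol and the reason in the SAP.
- Reconcile the visit schedule in SAP 6.4.1 with the protocol's Time and Events Schedule, so that each table has the right time points.

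The cost is a wording change and a few tables from data already collected. The real work is choosing and defending the two cut-offs.

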6.4.2. Columbia Suicide Severity Rating Scale (C-SSRS)

The C-SSRS is conducted during screening; at randomization; and after randomization every 2 weeks through Month 3, then every month through Month 6; at Months 8, 9, 10, and 12; then every 3 months through Month 54 (or at early termination). The C-SSRS is a measure of the spectrum of suicidal ideation and behavior that was developed in the National Institute of Mental Health Treatment of Adolescent Suicide Attempters Study to assess severity and track suicidal events through any treatment¹¹. It is a semi-structured clinician-administered questionnaire designed to solicit the occurrence, severity, and frequency of suicide-related ideation and behaviors during the assessment period.

The following are C-SSRS categories and have binary responses (yes/no). Each category is based on a direct question in the C-SSRS. The categories are ordered by increasing seriousness.

Suicidal Ideation (1-5)

- Category 1: Wish to be dead
- Category 2: Non-specific active suicidal thoughts
- Category 3: Active suicidal ideation with any methods (not plan) without intent to act
- Category 4: Active suicidal ideation with some intent to act, without specific plan
- Category 5: Active suicidal ideation with specific plan and intent

Suicidal Behavior (6-10)

- Category 6: Preparatory acts or behavior
- Category 7: Aborted attempt
- Category 8: Interrupted attempt
- Category 9: Non-fatal suicide attempt
- Category 10: Completed suicide

Self-injurious behavior without suicidal intent is also a C-SSRS outcome (although not suicide-related) and has a binary response (yes/no).

The Suicidal Ideation Score at a time point is the maximum suicidal ideation category with a “yes” response at that time point. A score of 0 is assigned if no suicidal ideation is present. The Suicidal Ideation Score ranges from 0 to 5.

The number and percentage of subjects with “yes” responses will be summarized for each category at each time point by treatment group. In addition, the number and percentage of subjects with any suicidal ideation, with any suicidal behavior, with either suicidal ideation or

behavior, and with any non-suicidal, self-injurious behavior will also be summarized at each time point and over the on-treatment period by treatment group.

The number and percentage of subjects meeting the following criteria will be summarized by treatment group:

- An increase in Suicidal Ideation Score from baseline at any post-baseline, time point in the // on-treatment period (treatment-emergent suicidal ideation compared to baseline).
- An increase in Suicidal Ideation Score from <4 at baseline to ≥ 4 at any post-baseline, time point in the on-treatment period (treatment-emergent serious suicidal ideation compared to baseline).
- An increase in Suicidal Ideation Score from 0 at baseline to ≥ 4 at any post-baseline, time point in the on-treatment period (emergence of serious suicidal ideation compared to baseline).

In these summaries, the denominator is the number of subjects meeting the baseline criterion.

Listings including additional C-SSRS details will be created for subjects with any suicidal ideation or behavior.

The above summaries will be presented for off-treatment time points, using the off-treatment baseline as the reference time point.

6.4.3. MRI (Magnetic Resonance Imaging)

All subjects will have an MRI during screening and after randomization at Months 6, 12, 24, 36 and 54 (or at early termination, if not performed at the previous visit). MRI image evaluation will be performed by a core imaging laboratory.

The number and percentage of subjects with evidence of a finding at any time during the double-blind period and at each time point will be summarized by treatment group for each of the following:

- ARIA-E (Amyloid-related imaging abnormalities which represent vasogenic edema and related extravasated fluid phenomena), including parenchymal hyperintensity, sulcal hyperintensity, and gyral swelling.
- ARIA-H (Amyloid-related imaging abnormalities which represent microhemorrhages and hemosiderin deposits), including microhemorrhages (mH), macrohemorrhages, and superficial siderosis.
- Lacunar infarct
- Territorial infarct outside of the cerebellum
- Full territory cerebellar infarct

Similar summaries for ARIA-E and ARIA-H finding will be provided. A listing of the subjects with any of the findings listed above will be provided.

Similar analyses will be performed for the off-treatment period.

